## 7.0 REGULATORY AND REPORTING REQUIREMENTS

The entities providing oversight of safety and compliance with the protocol require reporting as outlined below.

The Washington University Human Research Protection Office (HRPO) requires that all events meeting the definition of unanticipated problem or serious noncompliance be reported as outlined in Section 7.6.

The FDA requires that all serious and unexpected adverse events be reported as outlined in Section 7.7. In addition, any fatal or life-threatening adverse experiences where there is a reasonable possibility of relationship to study intervention must be reported.

CTI BioPharma, Inc. requires that all SAEs, irrespective of causal relationship, be reported as outlined in Section 7.8.

### 7.1 Definitions

#### 7.1.1 Adverse Events (AEs)

**Definition:** any unfavorable medical occurrence in a human subject including any abnormal sign, symptom, or disease.

**Grading:** the descriptions and grading scales found in the revised NCI Common Terminology Criteria for Adverse Events (CTCAE) version 4.03 will be utilized for all toxicity reporting. A copy of the CTCAE version 4.03 can be downloaded from the CTEP website.

**Attribution (relatedness), Expectedness, and Seriousness:** the definitions for the terms listed that should be used are those provided by the Department of Health and Human Services' Office for Human Research Protections (OHRP). A copy of this guidance can be found on OHRP's website:

<http://www.hhs.gov/ohrp/policy/advevntguid.html>

#### 7.1.2 Serious Adverse Event (SAE)

**Definition:** any adverse drug experience occurring at any dose that results in any of the following outcomes:

- Death
- A life-threatening adverse drug experience
- Inpatient hospitalization or prolongation of existing hospitalization
- A persistent or significant disability/incapacity (i.e., a substantial disruption of a person's ability to conduct normal life functions)
- A congenital anomaly/birth defect
- Any other experience which, based upon appropriate medical judgment, may jeopardize the subject and may require medical or surgical intervention to prevent one of the outcomes listed above

All unexpected SAEs must be reported to the FDA.

### **7.1.3 Unexpected Adverse Experience**

**Definition:** any adverse drug experience, the specificity or severity of which is not consistent with the current investigator brochure (or risk information, if an IB is not required or available).

Events that are both serious AND unexpected must be reported to the FDA.

### **7.1.4 Life-Threatening Adverse Experience**

**Definition:** any adverse drug experience that places the subject (in the view of the investigator) at immediate risk of death from the reaction as it occurred, i.e., it does not include a reaction that, had it occurred in a more severe form, might have caused death.

Life-threatening adverse experiences must be reported to the FDA.

### **7.1.5 Unanticipated Problems**

**Definition:**

- unexpected (in terms of nature, severity, or frequency) given (a) the research procedures that are described in the protocol-related documents, such as the IRB-approved research protocol and informed consent document; and (b) the characteristics of the subject population being studied;
- related or possibly related to participation in the research (“possibly related” means there is a reasonable possibility that the incident, experience, or outcome may have been caused by the procedures involved in the research); and
- suggests that the research places subjects or others at a greater risk of harm (including physical, psychological, economic, or social harm) than was previously known or recognized.

### 7.1.6 Noncompliance

**Definition:** failure to follow any applicable regulation or institutional policies that govern human subjects research or failure to follow the determinations of the IRB. Noncompliance may occur due to lack of knowledge or due to deliberate choice to ignore regulations, institutional policies, or determinations of the IRB.

### 7.1.7 Serious Noncompliance

**Definition:** noncompliance that materially increases risks, that results in substantial harm to subjects or others, or that materially compromises the rights or welfare of participants.

### 7.1.8 Protocol Exceptions

**Definition:** A planned deviation from the approved protocol that are under the research team's control. Exceptions apply only to a single participant or a singular situation.

Pre-approval of all protocol exceptions must be obtained prior to the event.

## 7.2 Reporting to the Human Research Protection Office (HRPO) at Washington University

The PI is required to promptly notify the IRB of the following events:

- Any unanticipated problems involving risks to participants or others which occur at WU, any BJH or SLCH institution, or that impacts participants or the conduct of the study.
- Noncompliance with federal regulations or the requirements or determinations of the IRB.
- Receipt of new information that may impact the willingness of participants to participate or continue participation in the research study.

These events must be reported to the IRB within **10 working days** of the occurrence of the event or notification to the PI of the event. The death of a research participant that qualifies as a reportable event should be reported within **1 working day** of the occurrence of the event or notification to the PI of the event.

## 7.3 Reporting to the Quality Assurance and Safety Monitoring Committee (QASMC) at Washington University

The PI is required to notify the QASMC of any unanticipated problem occurring at WU or any BJH or SLCH institution that has been reported to and acknowledged by HRPO as

reportable. (Unanticipated problems reported to HRPO and withdrawn during the review process need not be reported to QASMC.)

QASMC must be notified within 10 days of receipt of IRB acknowledgment via email to a QASMC auditor.

#### **7.4 Reporting to the FDA**

The conduct of the study will comply with all FDA safety reporting requirements. **PLEASE NOTE THAT REPORTING REQUIREMENTS FOR THE FDA DIFFER FROM REPORTING REQUIREMENTS FOR HRPO/QASMC.** It is the responsibility of the investigator to report any unanticipated problem to the FDA as follows:

- Report any unexpected fatal or life-threatening adverse experiences (Section 7.1.4) associated with use of the drug by telephone or fax no later than **7 calendar days** after initial receipt of the information.
- Report any serious, unexpected adverse experiences (Section 7.1.2), as well as results from animal studies that suggest significant clinical risk within **15 calendar days** after initial receipt of this information.

All MedWatch forms will be sent by the investigator or investigator's team to the FDA at the following address or by fax:

Food and Drug Administration  
Center for Drug Evaluation and Research  
Division of Oncology Drug Products  
[name]  
[name]  
FAX: [name]

#### **7.5 Reporting to CTI BioPharma, Inc.**

All SAEs, irrespective of causal relationship, must be reported to CTI using their SAE reporting form (Appendix D) within 24 hours of becoming aware of the event via either Fax or e-mail.

[contact]  
Email: [[contact]](mailto:[contact])

Special Considerations:

- SAEs considered to be related (ie, assessed as possibly, probably or definitely related) to study drug or study procedure by the investigator shall be followed until the event resolves, stabilizes or the patient is lost to follow up.

- SAEs assessed as unrelated to study drug or study procedures shall be followed for 30 days after last dose of study treatment, or until the event resolves, returns to baseline, stabilizes or the patient is lost to follow-up, whichever comes first.
- An SAE form should be completed for any event for which doubt exists regarding its seriousness. If an ongoing SAE changes in intensity, relationship to study drug, or as new information becomes available and/or known for the event, a follow-up SAE Report form should be completed and sent to the CTI within 24 hours of the change in SAE assessment.
- Any SAE that occurs after study completion and is considered by the investigator to be related to Tosedostat should be reported to CTI.

A narrative outlining the details of the SAE and treatment and outcome are to be included on the SAE form. The narrative must state whether there is a reasonable possibility that study drug caused the event. Follow-up information, such as laboratory reports, discharge summaries, autopsy reports, and information concerning outcome of the event, should be submitted as soon as the information becomes available.

#### **7.6 Timeframe for Reporting Required Events**

Reportable adverse events will be tracked for 30 days following the last day of study treatment.

### **8.0 PHARMACEUTICAL INFORMATION**

[figure not shown]
[REDACTED]

## 8.2 Capecitabine (Xeloda)

### 8.2.1 Capecitabine Description

Capecitabine is a fluoropyrimidine carbamate with antineoplastic activity. It is an orally administered systemic prodrug of 5'-deoxy-5-fluorouridine (5'-DFUR) which is converted to 5-fluorouracil.

The chemical name for capecitabine is 5'-deoxy-5-fluoro-N-[(pentyloxy) carbonyl]-cytidine and has a molecular weight of 359.35. Capecitabine has the following structural formula:

### 8.2.2 Clinical Pharmacology

Enzymes convert capecitabine to 5-fluorouracil (5-FU) *in vivo*. Both normal and tumor cells metabolize 5-FU to 5-fluoro-2'-deoxyuridine monophosphate (FdUMP) and 5-fluorouridine triphosphate (FUTP). These metabolites cause cell injury by two different mechanisms. First, FdUMP and the folate cofactor, N-methylenetetrahydrofolate, bind to thymidylate synthase (TS) to form a covalently bound ternary complex. This binding inhibits the formation of thymidylate from 2'-deoxyuridylate. Thymidylate is the necessary precursor of thymidine triphosphate, which is essential for the synthesis of DNA, so that a deficiency of

this compound can inhibit cell division. Second, nuclear transcriptional enzymes can mistakenly incorporate FUTP in place of uridine triphosphate (UTP) during the synthesis of RNA. This metabolic error can interfere with RNA processing and protein synthesis.

### **8.2.3 Pharmacokinetics and Drug Metabolism**

Following oral administration, capecitabine reached peak blood levels in about 1.5 hours (Tmax) with peak 5-FU levels occurring slightly later, at 2 hours.

Capecitabine and its metabolites are predominantly excreted in urine.

### **8.2.4 Supplier(s)**

Capecitabine is commercially available and will not be provided for by this study. Expenses associated with this drug will be billed to a third party payer as part of standard of care.

### **8.2.5 Dosage Form and Preparation**

Capecitabine is supplied as bioconvex, oblong film-covered tablets for oral administration. It is available in 150 mg and 500 mg tablets.

### **8.2.6 Storage and Stability**

Store at 25°C; excursions permitted to 15-30°C. Keep tightly closed.

### **8.2.7 Administration**

Capecitabine is an oral drug to be taken twice daily within 30 minutes after the end of a meal.

### **8.2.8 Special Handling Instructions**

Care should be exercised in the handling of capecitabine. Capecitabine tablets should not be cut or crushed. The use of gloves and safety glasses is recommended to avoid exposure in case of breakage of tablets. If powder from broken capecitabine tablets contacts the skin, wash the skin immediately and thoroughly with soap and water. If capecitabine contacts the mucous membranes, flush thoroughly with water.

## **9.0 CORRELATIVE STUDIES**

### **9.1 Proteomic samples**

Samples will be collected for consideration of proteomic evaluation. Serum and plasma samples will be collected at the following time points:

- Baseline
- Day 1 of each cycle beginning on Cycle 2 before dosing capecitabine and tosedostat

All samples will be taken to [name] laboratory after they are drawn. For the plasma proteomic studies, collect 10 mL of blood in a lavender top K2EDTA tube with a Hemogard stopper. After collection of whole blood into the EDTA tube, gently invert the tube 10 times. Centrifuge the blood samples immediately under refrigerated conditions (2-6°C) at 1300 x g for 10 minutes. Remove plasma into a 40 mL conical tube and leave approximately 1 mL of plasma overlaying the cells. Centrifuge the sample at 2400 x g for 15 minutes. Transfer aliquots (0.5 mL) to the cryovials and store at -70°C until analysis

For the serum proteomic studies, collect 10 mL of blood in a red top silica clot activator serum tube with a conventional stopper. The blood sample is allowed to sit upright for 30 minutes at room temperature. Centrifuge blood samples under refrigerated conditions at 1300 x g for 10 minutes. Remove the serum into a 40 mL conical tube and leave the residual serum so as not to disturb the clot. Centrifuge the sample at 2400 x g for 15 minutes. Transfer aliquots (0.5 mL) to the cryovials and store at -70°C until analysis.

## **9.2 Tumor Specimen Collection**

### **9.2.1 Archived Formalin Fixed Paraffin Embedded Tissue Samples**

Formalin fixed paraffin embedded (FFPE) samples from previous diagnostic or therapeutic procedures for the tumors will be requested. Tissue blocks are preferable; however, if the tissue block cannot be obtained, 20 unstained slides sectioned at 5 microns will be required. Tumor samples must be from one FFPE block containing viable tumor with tumor cells from the primary pancreatic tumor. Tumor cells must account for at least 10% of cell nuclei in the tumor-containing regions of the block. Unacceptable specimens include specimens processed using acid decalcification (EDTA is acceptable); tumor cellularity less than 10% in tumor involved regions of the specimen; and frozen specimens. Minimum sample volume is 3-1mm punches (cores); 5-5µm scrolls; or 10-5µm slides. Storage/transport conditions: FFPE blocks: ambient /room temperature. Place in a sealed container (bag).

Next generation sequencing is performed on all coding regions of ABL1, AKT1, ALK, APC, ASXL1, ATM, BRAF, CEBPA, CTNNB1, DNMT3A, ERBB2, EGFR, ESR1, FGFR4, FLT3, IDH1, IDH2, JAK2, KIT, KRAS, MAPK1(ERK), MAP2K2(MEK), MET, KMT2A(MLL), MPL, MYC, MYD88, NOTCH1, NPM1, NRAS, PDGFRA, PIK3CA, PTEN, PTPN11, RB1, RET, RUNX1, STK11, TET2, TP53, VHL and WT1 to detect single nucleotide variants and small insertions and deletions; selected introns of ALK and KMT2A(MLL) to

detect rearrangements. Next generation sequencing will be performed on initial tumor biopsies.

A GPS requisition form is obtained and completed from the Washington University Genomics and Pathology Services.

### **9.2.2 Tumor Biopsy (optional)**

After Cycle 2, patients will have the option of having another biopsy of the pancreatic tumor or metastatic site to correlate with treatment response. Patients who have a PR will be required to undergo biopsy if deemed safe for the patient and tissue is feasible to obtain.

Fresh tumor samples will be obtained where feasible by CT or ultrasound-guided core biopsy. The samples will be snap frozen for future comprehensive genomic analysis. All biopsy samples will be processed and stored in the PI's lab.

### **9.2.3 Evaluation of genetic alternations that potentially associated with treatment response**

Pancreatic cancer, as all human malignancies, is caused by genetic mutations. Mutations in *KRAS*, *P16*, *TP53* and *SMAD4* genes are common (1821). With the advent of improved sequencing techniques, the identification of several key genetic alterations has led to the development of targeted therapies, such as imatinib and numerous EGFR-targeted therapies (cetuximab, erlotinib). Identifying the key genetic alterations in pancreatic cancer may lead to a better understanding of carcinogenesis and the development of more effective therapies. It is also important to analyze the somatic mutations and correlate them with treatment response and overall survival as there may be certain genetic alterations that prove to be more chemosensitive to certain drugs than others.

The Genomics and Pathology Service at Washington University (GPS@WU) offers next-generation sequencing of tumor somatic mutations in 42 oncogenes, tumor suppressors, and other cancer genes. The rationale for performing next generation sequencing is to identify the key genetic alterations in each patient's tumor. This information can then be used to compare patients' clinical information to see if there is a correlation between response rates, overall survival, and specific genetic mutations.

Next generation sequencing is performed on all coding regions of ABL1, AKT1, ALK, APC, ASXL1, ATM, BRAF, CEBPA, CTNNB1, DNMT3A, ERBB2, EGFR, ESR1, FGFR4, FLT3, IDH1, IDH2, JAK2, KIT, KRAS, MAPK1(ERK), MAP2K2(MEK), MET, KMT2A(MLL), MPL, MYC, MYD88, NOTCH1, NPM1, NRAS, PDGFRA, PIK3CA, PTEN, PTPN11, RB1, RET, RUNX1, STK11, TET2, TP53, VHL and WT1 to detect single nucleotide variants and small insertions and deletions; selected introns of ALK and KMT2A(MLL) to

detect rearrangements. Next generation sequencing will be performed on initial tumor biopsies.

A GPS requisition form is obtained and completed from the Washington University Genomics and Pathology Services

#### **9.2.4 Assessment of Amino Acid Deprivation Response**

Tosedostat's proposed mechanism of action is to deplete amino acids to limit production of new proteins and to stimulate a stress response (amino acid deprivation response), which leads to increased apoptosis. Autophagy is the process by which cells deliver cellular materials to lysosomes for digestion and autophagy is proposed to be increased in cells with nutrient deprivation (24). The kinase mTOR is a critical regulator of autophagy induction and autophagy-related (Atg) genes help control autophagosome formation. Numerous gene products involved in autophagy, such as ATG5, ATG8, and Beclin-1 can be assessed by immunohistochemistry. The slides will be stained for metalloproteases such as APN/CD13 and autophagy markers, which may include but are not limited to, ATG 8, ATG 5, and Becline.

### **9.3 Pharmacokinetic Studies**

Serum will be collected from the patients in the phase I portion of the study at baseline and on Cycle 2 Day 1 in the event of unexpected toxicities to evaluate the pharmacokinetics.

## 10.0 STUDY CALENDAR

Baseline evaluations are to be conducted within 14 days prior to start of protocol therapy. Scans and x-rays must be done no more than 3 weeks prior to the start of the protocol therapy. Cycles are 21 days. All study visits must occur within +/-3 days of the time indicated on the calendar (with the exception of ECHOs which must be resulted 7 days prior to Day 1 treatment).

|                                       | Screening | Baseline | D1 of each cycle | End of C2      | End of each even-numbered cycle | F/UA           |
|---------------------------------------|-----------|----------|------------------|----------------|---------------------------------|----------------|
| Informed consent                      | X         |          |                  |                |                                 |                |
| H&P, VS, wt, ECOG PS                  | X         |          | X                |                |                                 |                |
| CBC I                      | X         |          | X I   |                |                                 |                |
| CMP I                      | X         |          | X I   |                |                                 |                |
| β-hCG C                    | X         |          |                  |                |                                 |                |
| CA19-9                                | X         |          | X                |                |                                 |                |
| Troponin-I or T                       | X         |          | X                |                |                                 |                |
| BNP                                   | X         |          | X                |                |                                 |                |
| ECHO or MUGA K             | X         |          | X J   |                |                                 | X B |
| ECG                                   | X         |          | X D   |                |                                 | X B |
| CT scan                               | X         |          |                  |                | X                               |                |
| Tosedostat                            |           |          | X G   |                |                                 |                |
| Capecitabine                          |           |          | X H   |                |                                 |                |
| Research blood for proteomics         |           | X        | X E   |                |                                 |                |
| Research blood for PKs (phase 1 only) |           |          | X F   |                |                                 |                |
| Archival tissue L          |           | X        |                  |                |                                 |                |
| Fresh biopsy                          |           |          |                  | X M |                                 |                |
| AE assessment N            |           | X        | X                |                |                                 | X              |

A: Every 3 months for 1 year

B: 1 month after end of study treatment, then every 6 months until the study closes

C: Women of childbearing potential only

D: ECG will be done weekly during Cycle 1. If ECGs are normal (or abnormal, but not related to study drug and/or clinically significant), ECGs will only be required on Day 1 of each cycle starting Cycle 2. However, if cycle 1 ECGs are abnormal and related to study drug, continue weekly ECGs.

E: Not drawn on C1D1

F: C2 only

G: Daily on Days 1-21 of each cycle

H: Daily on Days 1-14 of each cycle

I: Weekly during Cycle 1 of Phase I

J: The screening assessment will count as the C1D1 assessment

K: Echocardiogram preferred; prior approval from PI or designee required for MUGA

L: If available, archival tissue to be provided

M: Patients who have a PR will be required to undergo biopsy if deemed safe for the patient and tissue is feasible to obtain.

N: From baseline through 30 days after treatment ends.

## 11.0 DATA SUBMISSION SCHEDULE

Case report forms with appropriate source documentation will be completed according to the schedule listed in this section.

| Case Report Form                                       | Submission Schedule                                               |
|--------------------------------------------------------|-------------------------------------------------------------------|
| Original Consent Form                                  | Prior to registration                                             |
| Registration Form
Eligibility Form
On-Study Form | Prior to starting treatment                                       |
| Treatment Form
Correlatives Form                    | Every cycle                                                       |
| DLT Form                                               | End of Cycle 1                                                    |
| Toxicity Form                                          | Continuous                                                        |
| Treatment Summary Form                                 | Completion of treatment                                           |
| Follow Up Form                                         | Every 3 months for 1 year after end of treatment                  |
| Tumor Measurement Form                                 | Baseline, end of every even numbered cycles, and end of treatment |
| MedWatch Form                                          | See Section 7.0 for reporting requirements                        |

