## **2.0 OBJECTIVES**

### **2.1 Primary Objectives**

1. Phase I: To determine the recommended phase II dose (RP2D) and dose-limiting toxicities (DLTs) of tosedostat and capecitabine combination therapy in patients with advanced or metastatic pancreatic cancer.
2. Phase II: To determine progression-free survival (PFS) rate at 3 months of tosedostat and capecitabine combination therapy in patients with advanced or metastatic pancreatic cancer.

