### 5.5.4 Toxicity, Response, and DLT Evaluations

All patients who receive any study treatment are evaluable for toxicity. Patients are evaluated from first receiving study treatment until a 30-day follow up after the conclusion of treatment or death.

All patients are evaluable for disease response unless they come off study due to treatment related adverse events(s) prior to completion of Cycle 2 and have not had any disease assessment.

A patient is evaluable for DLT assessment only if enrolled in the phase I portion and only during Cycle 1 of treatment. If the patient is not able to be treated on Day 1 of Cycle 2, then s/he is still considered in Cycle 1 active treatment and can experience a DLT. Once the patient has been treated in Cycle 2, s/he will no longer be evaluated for DLTs in all subsequent cycles.

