## 6.0 DOSE DELAYS/DOSE MODIFICATIONS

### 6.1 Tosedostat Dose Reduction Table

|               |                 |
|---------------|-----------------|
| Starting Dose | 120 mg po daily |
| Dose Level -1 | 60 mg po daily  |

Patients will be monitored for toxicity and the dose of tosedostat may be adjusted. Dose reduction by one dose level will be allowed. Patients requiring more than one dose reduction will be discontinued from the study.

Recommended dose reductions for tosedostat are to decrease the current dose by 60 mg. The lowest dose available is 60 mg. Doses may be held as needed for toxicity resolution during a cycle. Doses omitted for toxicity are not replaced or restored within the same cycle (meaning that the cycle remains 21 days regardless of the number of doses of taken). If a patient experiences toxicity which has not resolved to grade 2 or lower within two weeks, treatment with tosedostat should be permanently discontinued.

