### 6.1.2 Hematologic Toxicity

ANC must be  $\geq 1,000$  cells/ $\mu$ l and platelet count must be  $\geq 75,000$  cells/ $\mu$ l at the start of each cycle.

| Grade                      | Occurrence      | Tosedostat                                                        |
|----------------------------|-----------------|-------------------------------------------------------------------|
| Neutrophils         |                 |                                                                   |
| Grade $\leq 2$             | Any             | Current dose                                                      |
| Grade 3                    | Any             | Hold till ANC $\geq 1,000$ , resume the current dose              |
| Grade 4                    | 1 st | Hold till ANC $\geq 1,000$ , resume the next lower dose           |
| Grade 4                    | 2 nd | Discontinue                                                       |
| Platelets           |                 |                                                                   |
| Grade $\leq 1$             | Any             | Current dose                                                      |
| Grade 2                    | Any             | Hold till platelets $\geq 75,000$ , resume the current dose level |
| Grade 3                    | Any             | Hold till platelets $\geq 75,000$ , resume the next lower dose    |
| Grade 4                    | 1 st | Hold till platelets $\geq 75,000$ , resume the next lower dose    |
|                            | 2 nd | Discontinue                                                       |
| Febrile neutropenia |                 |                                                                   |
| Grade 3                    | 1 st | Hold till ANC $\geq 1,000$ , resume the next lower dose           |
|                            | 2 nd | Discontinue                                                       |

The patient will be taken off the trial if more dose reductions are called for than are allowed.

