## 12.0 MEASUREMENT OF EFFECT

### 12.1 Antitumor Effect – Solid Tumors

For the purposes of this study, patients should be re-evaluated for response every 6 weeks. In addition to a baseline scan, confirmatory scans should also be obtained 6 weeks (not less than 4) weeks following initial documentation of objective response.

Response and progression will be evaluated in this study using the new international criteria proposed by the revised Response Evaluation Criteria in Solid Tumors (RECIST) guideline (version 1.1) [Eur J Ca 45:228-247, 2009]. Changes in the largest diameter (unidimensional measurement) of the tumor lesions and the shortest diameter in the case of malignant lymph nodes are used in the RECIST criteria.

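### After a late cycle start the plan does not say whether scans stay 6-weekly or follow cycles; if they follow cycles, the 3-month PFS rate can be read too high

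*Combined protocol and SAP*

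**What the plan says.** The phase II objective in section 2.1 is "To determine progression-free survival (PFS) rate at 3 months". Section 12.4.5 measures PFS from the start of treatment.

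Scan timing appears in three places:

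- The CT row of the study calendar (10.0) is marked under "End of each even-numbered cycle". The calendar sets 21-day cycles and adds: "All study visits must occur within +/-3 days of the time indicated on the calendar".
- The Tumor Measurement Form line in 11.0 reads "Baseline, end of every even numbered cycles, and end of treatment".
- Section 12.1 says "patients should be re-evaluated for response every 6 weeks".

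The plan foresees delay. Section 5.5.4 covers the case "If the patient is not able to be treated on Day 1 of Cycle 2", for phase I DLT evaluation. Section 5.8 refers to treatment delays caused by adverse events. Section 6.1.2 sets neutrophil and platelet thresholds to be met "at the start of each cycle".

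It also limits delay. When tosedostat doses are omitted, "the cycle remains 21 days regardless of the number of doses of taken" (6.1). Omitted capecitabine doses are not made up, and either drug may continue while the other is held (6.2).

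**The concern.** Two timing rules serve the primary endpoint, one counted in cycles and one in weeks. Once a cycle starts late they separate, and nothing says which one applies. A site that schedules from the calendar would move the scan with the cycle.

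The second scan has little room to move before 3 months. If it slips past the landmark, a delayed patient's 3-month status rests on scan 1 alone. A patient who progresses between scan 1 and the landmark is then counted as progression-free at 3 months. The error goes one way, the trial has no control arm to share it, and the analyst cannot recover a scan that was not done.

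**Working it through.** **Schedule.** Two cycles are 2 × 21 = 42 days, which is 6 weeks, so the two rules reproduce each other when all cycles start on time. Scan 2 then falls on day 4 × 21 = 84.

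**Margin to the landmark.** The plan does not give 3 months in days. Assume 3 × 365.25/12 = 91.3 days.

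- Nominal margin: 91.3 − 84 = 7.3 days. A cumulative delay of 7 days puts scan 2 on day 91 (in time); 8 days puts it on day 92 (late).
- With the ±3-day window: 91.3 − 87 = 4.3 days to 91.3 − 81 = 10.3 days.
- If 3 months means 89 to 92 days, the nominal margin is 5 to 8 days. If it means 12 weeks, it is zero.

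**Size: inputs.** The medians of 2.0 and 4.0 months come from 14.1. The rest is assumed: exponential PFS, progression found only at scheduled scans and dated at the scan that finds it, a 14-day cumulative delay, and a share f = 10, 20 or 30% of patients delayed. The documents give no delay rate.

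**Formula.** S(t) = 2^(−t/m), with m = 60.875 days (2.0 months) or 121.75 days (4.0 months). With a 14-day delay, scan 2 is on day 98. The last scan before the landmark is scan 1, on day 42 if the delay comes wholly after it, or day 56 if wholly before it.

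| | 2.0 months | 4.0 months |
|---|---|---|
| S(42) | 62.0% | 78.7% |
| S(56) | 52.9% | 72.7% |
| S(84), reading with on-time scans | 38.4% | 62.0% |
| S(91.3), true value | 35.4% | 59.5% |

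Shift = f × (S(last scan) − S(84)). For example, at 2.0 months and f = 20%: 0.20 × (52.9 − 38.4) = 2.9 points to 0.20 × (62.0 − 38.4) = 4.7 points.

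| Share delayed | Shift, 2.0 months (points) | Shift, 4.0 months (points) |
|---|---|---|
| 10% | 1.4-2.4 | 1.1-1.7 |
| 20% | 2.9-4.7 | 2.1-3.3 |
| 30% | 4.3-7.1 | 3.2-5.0 |

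A simulation of 400,000 patients per median, with the delay split uniformly before and after scan 1, read 40.3, 42.2 and 44.1% at 2.0 months and 63.4, 64.7 and 66.1% at 4.0 months. These lie inside the ranges above.

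**Allowing for deaths.** If 30% of events are deaths with exact dates, multiply the shifts by 0.7. At 20% delayed they become 2.0-3.3 points (2.0 months) and 1.5-2.3 points (4.0 months).

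**Scale.** The standard error of a 38.4% rate in 36 patients is √(0.384 × 0.616/36) = 0.081, about 8 points. At 20% delayed, the unadjusted shift is 36 × 0.029 to 36 × 0.047, or 1.0 to 1.7 patients, at 2.0 months. At 4.0 months it is 36 × 0.021 to 36 × 0.033, or 0.8 to 1.2 patients.

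**The case against.** The best reply is that 12.1 already answers the question. It is the section on measuring effect and states a 6-week interval for this study, whereas 11.0 only schedules forms. On that reading scan 2 stays at day 84 and there is no problem. The reading is reasonable, but the calendar's CT row is tied to cycles, and no text ranks 12.1 above it.

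The trigger is also narrow. A reader might infer that any dose hold moves the scans. The documents do not support that: omitted tosedostat doses leave the cycle at 21 days, a patient who omits capecitabine resumes the planned cycle, and one drug can continue without the other. Section 5.5.4 speaks only to phase I Cycle 1. What remains is mainly the count thresholds in 6.1.2.

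The calculated shifts are high for the stated delay rates. Some delayed patients would leave treatment and have an end-of-treatment measurement before the landmark. Section 12.4.3 asks for efforts to document progression after discontinuation. Patients with undetected progression who die before the landmark still count as events. This objection stands, and the figures are an upper illustration.

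On-time scans also leave a gap, 38.4% against 35.4% or 62.0% against 59.5%, and settling the scan rule does not remove it.

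**Conclusion.** The gap is real and touches the primary endpoint, but its expected effect is small. Under cycle-tied scanning, a cumulative start delay of more than about 7 days (about 4 to 10 with the visit window) moves scan 2 past the landmark and biases the 3-month PFS rate upward. The illustrated range, about 1-7 points at a 2.0-month median and 1-5 at 4.0 months, depends on the assumed delay and delay rates and on progression being found only at scheduled scans.

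Three stronger conclusions are tempting and not supported:

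- That the two rules contradict each other outright. They coincide whenever cycles start on time.
- That the trial's decision is compromised. Section 14.1 powers on median PFS and calls phase II a pilot, and the plan sets no pass mark on the 3-month rate.
- That patients who stop without progression add to the upward bias. The plan states no PFS censoring rule, so the direction for them cannot be established.

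This is a worthwhile, inexpensive improvement to the reported estimate.

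**What to change.** Reconcile 10.0 and 11.0 with 12.1 so that tumor assessments fall every 6 weeks from Cycle 1 Day 1, within ±3 days, regardless of cycle delays. In 14.2, define the 3-month landmark in days and its assessment window, day 84 ± 3 days.

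Optionally, add a sensitivity analysis in 14.2 that counts patients as not progression-free at 3 months if they have no scan in that window and no later scan showing them free of progression. If scans were still tied to cycles, this would read (1 − f) × S(84) + f × S(98), with S(98) = 32.8% or 57.2%. That gives 37.9, 37.3 and 36.7% at 2.0 months, and 61.5, 61.0 and 60.6% at 4.0 months, for 10, 20 and 30% delayed. It is conservative: if 10% of patients stop by day 84 independently of progression and have no later imaging, it falls by up to 0.10 × S(84), or 3.8 points (2.0 months) or 6.2 points (4.0 months).

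The cost is a calendar footnote, one line in the form schedule and a short addition to 14.2. In delayed patients, scans may fall mid-cycle, may separate from the end-of-Cycle-2 biopsy, and may be slightly more frequent per cycle than under cycle-tied scanning.
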